The study consists of two phases corresponding to two aims. For Aim 1 we will develop a modularized, functionally-tailored oral care intervention based on literature review and CG interview input. We anticipate eight training modules that can be used alone or in varying combinations to provide functionally-appropriate oral care rehabilitation for PWD and needbased skills training to their family CGs. These will be adapted from Mouth Care Without a Battle, a validated oral hygiene intervention developed for NH residents with dementia. Aim 2 will examine the efficacy and feasibility of the proposed intervention using a randomized controlled design among 40 PWD/CG pairs. After baseline assessment, a 4-week, dyadic, hands-on, functionally-tailored oral care intervention will be delivered to 20 PWD/CG dyads. Control group participants (n=20) will receive the oral hygiene education that is commonly provided to PWD during dental care. Data collection will occur at baseline, 4-weeks and 3 months. Differences between the control and intervention groups with regard to PWD outcomes (e.g., oral hygiene and behavior symptoms during oral care), caregiver outcomes (e.g., burden, self-efficacy) and the care partner relationship will be explored.

This protocol has been developed to guide the study of Aim I and the Aim II study.

IV. Eligibility, Enrollment, and Consent

Sources of Recruitment. Tentatively, the study participants will be recruited from the sites listed below. The site names and IDs are as follows:

Table 2 recruitment sites and ID

Recruitment site	Site ID
Phase I study	10
Dementia registry	20
UI Memory Care Clinic ([name])	30
UI Dental School	40
UI Geriatric Clinic ([name]/[name])	50
Local Community (mass email)	60
UIHC list (TrinetX)	70
Mercy Caregiver Group	80
Huntington's Clinic	90
Mercy Center for Memory Health	11
Heritage Area Agency on Aging	12

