1	 Program overview Dyad education Goal identification Need assessment 	 Through dyad's demonstration, OCC assesses dyad's oral care skills (e.g., tooth brushing with disclosing solution and denture care, if applicable), preferences (e.g., floss vs. interdental brush), related challenges, and needs for adaptive oral hygiene products (specially-designed toothbrush, mouth prop) Assesses need for environmental changes (e.g., lighting, contrast, set-up of oral care products) Complete the rest of the items in the First visit assessment 				
000	develops function	form nally-tailored intervention plan to enhance what is currently				
		ng and compensate what needs to improve				
		Reviews intervention plan and materials				
	•Tooth brushing •Denture care (if applicable) •Interdental brushing •Dry mouth care	 Works with dyads to develop mutually agreed upon oral care plan (e.g., when and how often to perform oral care, use of oral care products) Module 2.0 				
		 Works with dyad to eliminate environmental obstacles Module 4.1 and other Modules and Scenarios as identified. 				
2		 Reviews personalized oral hygiene products (e.g., special toothbrush, toothpaste, or mouth prop) with dyad. 				
		Following the previously designed intervention plan, delivers hands-on, basic oral care (tooth brushing, denture care) and related skills training (e.g., cueing, quality improvement, behavior management as needed) via the trial & error strategy (tailor to dyad's needs and repeat until dyad demonstrates and fully learns the skills) Polivers delivered byginne long and instructions.				
		 Delivers daily oral hygiene logs and instructions. Review, discuss, and reinforce the basic skill set learned at the last visit. 				
		Review and reinforcement daily oral hygiene log				
3		 Review and reinforcement daily oral hygiene log Review oral care products required for interdental brushing, and dry mouth care. 				
		 Delivers training on cleaning between teeth, and dry mouth management. 				
		 Provide hand-on practice and real time feedback until dyads fully learn the skills. 				
	 Advanced skills reinforcement Program review, and wrap-up 	Reviews dyad's progress to date.				
		 OCC assesses and gives feedback of a dyad's final demonstration of oral care skills with disclosing solution. 				
4		 Review, discuss, and reinforce basic and advanced skill sets and tailor skills as needed. Discuss Modules that have not been reviewed, if necessary. 				

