		Trainer and dyad work together to develop maintenance plan (with the minimum goal of once-a-day oral care)				

• Distributes the educational packet and resources for future use.

Control group:

Control group will have 3 visits: Initial visit, 4th week and F/U at 3 months. Control dyads will receive a 15-minute, home-based, untailored oral care training, using only Module 1 and Control Group OHI Module 2.7, in the first visit. After a demonstration, the OCC should allow participating dyads time to practice the oral care skills and provide real time feedback for the participants. After the demonstration, the1 Care recipient Feasibility Evaluation Questionnaire (if applicable) and the Caregiver Feasibility Evaluation questionnaire should be completed.

VII. Data Collection

[figure not shown]
Validation study.

The oral care coach (OCC) and research assistant (RA) will visit participants. The following data (Table 5.) needs to be collected during the validation study. Some of the data will be collected multiple times. Specifically, to avoid overburden to the study participants, the study coordinator should arrange an appointment before the intervention to collect all the baseline data. All the interviews and assessments should be given in a relaxed, comfortable environment and format. Breaks should be given if participants become tired, anxious or frustrated.

[figure not shown]
If a subject is identified as in need of immediate dental attention in the oral exam or during the intervention, the research assistant or OCC will document and communicate this need to the study coordinator. In accordance with approved IRB procedures and the data safety monitoring plan, the study coordinator will then send the consenting party a standardized notice recommending a follow-up examination. If needed, the identified issue will be reported to the IRB and the data safety monitoring committee.

[figure not shown]
The assessments should be given in the following order:

Visit 0

[figure not shown]
Visit 4

Visit 3-month

Dyad dy

^{*}if experimental group, collect and review oral care log before starting

Table 5. Data to be collected in the validation study

Data	Measure/Tool	Subject	Time	Examiner
Oral self-care function	Dental Activities Test (DAT)	PWD	Baseline	RA
Cognition	MMSE New cognitive screening tool (NCST) Mini-Cog	PWD	Baseline	RA
Daily function	ADL and IADL	FCG	Baseline	RA
Depression	Visual analogue scaleCESD depression scale	PWD	Baseline	RA

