Apathy	Dementia Apathy Interview and Rating	FCG	Baseline	RA
Anosognosia	AnosognosiaSelf-perceived oral health	PWD/FCG	Baseline	RA
Oral hygiene	Plaque index Gingival index	PWD	Baseline 4-week follow-up 3-month follow-up	Dentist
 Sociodemographics Medical history & medication Dental care pattern 	Caregiver Interview	FCG	Baseline	RA OCC
 Oral hygiene practice Perceived oral hygiene and oral health Behavior symptoms during oral care Mouth Care Related Caregiver Burden Dyadic relationship 	Caregiver Interview	FCG	Baseline4-week follow-up3-month follow-up	LD &RA
CG efficacy in providing oral care	Caregiver Self-efficacy Scale	FCG	Baseline4-weekfollow-up3-monthfollow-up	RA
First visit assessment	First visit assessment form	PWD/FCG	1 st visit	LD
Feasibility assessment (session)	 Care recipient Feasibility Evaluation Questionnaire Caregiver Feasibility Evaluation Questionnaire 	PWD/FCG	Every session	LDRA
Trainer assessment	Trainer evaluation questionnaire	Trainer	Every session	LD
Daily oral care practice	Daily oral care log	PWD/FCG	Every session3-month follow-up	LD

Feasibility assessment (program)	•	Care recipient Program Feasibility Evaluation Questionnaire Caregiver Feasibility Program Evaluation Questionnaire	PWD/FCG	4-week follow-up	RA
Implementation assessment	•	Training log & trainer interview	Trainer	Every session	XC

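### An oral care log review for the experimental arm only appears to precede the 3-month caregiver reports

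*Protocol*

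**What the plan says.** Section VII of the Protocol (Data Collection) introduces the visit sequences with "The assessments should be given in the following order". The headings Visit 0, Visit 4 and Visit 3-month follow. After the last of them comes a footnote: "if experimental group, collect and review oral care log before starting". The lists themselves, and the item that carries the asterisk, are in figures not visible in the text available. That is a limit of the text and not a fault of the plan.

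Other places that bear on the footnote:

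- **Section III, Aim 2.** "Data collection will occur at baseline, 4-weeks and 3 months".
- **Section VI, session table.** At session 2 the coach "Delivers daily oral hygiene logs and instructions". Session 3 lists "Review and reinforcement daily oral hygiene log".
- **Section VI, control group.** "Control group will have 3 visits: Initial visit, 4th week and F/U at 3 months". The control description mentions no log.
- **Table 5.** The entry "Daily oral care log" is scheduled for every session and for the 3-month follow-up. The caregiver interview and the caregiver self-efficacy scale are scheduled at baseline, 4 weeks and 3 months.
- **SAP.** Wilcoxon rank-sum tests compare the arms at each visit and, for the primary outcomes, compare raw and percent change from baseline to 4 weeks and to 3 months.

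**The concern.** A between-arm comparison of self-reports assumes that both arms report under the same conditions. Here one arm appears to go through a record of its recent oral care just before being asked about oral care, and the other arm does not.

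The overlap is most direct for oral hygiene practice, because daily oral care practice is what Table 5 says the log records. Perceived oral hygiene, behavior symptoms, burden, the dyadic relationship and self-efficacy are also reported by the caregiver, and the same review could color them.

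At stake is whether a 3-month difference on these outcomes reflects the intervention or partly the conditions of the interview. This part of the problem is avoidable, because it depends only on the order of steps within a visit.

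**Working it through.** There is no stated figure to reproduce. The check is a reading of the passages against each other, followed by a count.

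**1. Which arm.** The footnote is conditional on the experimental group. The supplied text describes no log and no equivalent step for controls. The session table that issues the log is captioned for the control group, but its four tailored sessions match the study group and conflict with the control description. The caption looks like a labeling slip and does not change the reading.

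**2. Which visit.**
- An arm condition is needed only at a visit that both arms attend. Controls attend the initial visit, week 4 and month 3.
- Logs are first issued at session 2, after the baseline appointment, so baseline is ruled out.
- *3 months:* well supported. The footnote is printed directly after that heading, and Table 5 lists the log there.
- *4 weeks:* uncertain. The three headings line up with the three data-collection points in section III, which favors including it. Against that, training session 4 carries the same number, and Table 5 gives the log no separate 4-week entry.

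**3. Before what.** The anchor is missing, so what is about to start has to be inferred. The natural reading is the assessments of that visit, since the footnote belongs to the assessment order.

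**4. What is reported at follow-up.** Outcomes that Table 5 repeats at 4 weeks and 3 months:

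| Source | Outcomes | Number |
|---|---|---|
| Dentist | plaque index, gingival index | 2 |
| Caregiver interview | practice; perceived hygiene and health; behavior symptoms; burden; dyadic relationship | 5 |
| Self-efficacy scale | caregiver self-efficacy | 1 |
| **Total** | | **8** |

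Caregiver-reported: 5 + 1 = 6 of 8 (75%).

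**5. Possible reach.** As planned, 20 of 20 experimental dyads and 0 of 20 control dyads get the step. At 3 months, 6 of 8 outcomes could follow it. Counting both follow-up visits gives 8 × 2 = 16 outcome-by-visit comparisons. Of these, 6 × 1 = 6 (37.5%) are exposed if the footnote covers 3 months only, and 6 × 2 = 12 (75%) if it also covers the 4-week assessment. These are counts of what might follow the review. They do not measure an effect, and 16 is not the number of tests in the SAP.

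**6. Can the analysis remove it?** Let d be a reporting shift caused by the review, present only in the experimental arm and only at follow-up. Let B be an experimental caregiver's baseline score and Y the follow-up score that would be given without the review.
- *Each visit:* experimental scores Y + d are compared with control scores that contain no d. The shift stays in the difference.
- *Raw change:* (Y + d) − B = (Y − B) + d. Baseline contains no d, because no log existed then, so nothing cancels.
- *Percent change:* 100(Y + d − B)/B = 100(Y − B)/B + 100d/B. The term in d remains.

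No value or sign is assigned to d, because the documents give none.

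**The case against.** The strongest objection is that the key premise is not visible. Bias requires the review to come before the caregiver interview and the self-efficacy scale, and the lists that would show this are missing. The asterisk could mark the whole visit, or one item placed after the interview. This stands. The order is inferred, and the point has to be conditional. With the lists missing, the absence of a visible control step is also weaker evidence than it would otherwise be.

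Second, Visit 4 may be training session 4. Log review there would be part of the treatment under test. This also stands, and it is why the point centers on 3 months. The argument does not carry over to 3 months, which falls after the 4-week intervention. If a review then is meant as treatment, the Protocol should say so.

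Third, experimental caregivers have already had four coached sessions and kept logs, so their reports differ in prompting and expectation anyway, and nothing shows that one more review adds materially. This is fair as to size. It does not justify an avoidable difference immediately before measurement.

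Fourth, no between-arm test could separate a step given wholly to one arm. That is correct, so the remedy lies in the visit procedure and not in the choice of test.

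Fifth, the aims are exploratory: differences in "PWD outcomes (e.g., oral hygiene and behavior symptoms during oral care), caregiver outcomes (e.g., burden, self-efficacy) and the care partner relationship will be explored". This limits the weight of the point but does not remove it. Four of the five outcomes named there are caregiver-reported, though they are given as examples and not as a full list.

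**Conclusion.** The point holds in a conditional form, mainly for the 3-month visit. On the natural reading of the footnote, experimental caregivers review their log before the 3-month assessments and controls have no counterpart. If that review precedes the caregiver interview and the self-efficacy scale, up to 6 of the 8 repeated outcomes are reported under unequal conditions, and the planned comparisons cannot correct for it. Extension to the 4-week assessment is possible but not established.

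Four stronger conclusions might be inferred, and the documents do not support them:

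- **That the review inflates the apparent benefit.** Direction is unknown. A review may prompt better answers, or bring missed days and strain to mind. Session 3 pairs log review with reinforcement, but the footnote mentions only collecting and reviewing.
- **That the plaque and gingival scores are biased.** They are scored by a dentist, and no route to them is shown.
- **That the primary result is affected.** The SAP text available does not name the primary outcomes.
- **That the review unblinds the interviewer.** Table 5 gives one examiner code for the log and lists the same code, with the research assistant, for the caregiver interview, so one person may do both. Who does what at the 3-month visit is not stated.

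The correction is worth making because it is cheap and specific. Confidence is moderate, because the order rests on inference.

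**What to change.** Amend the footnote in section VII so that the log is reviewed only after all outcome assessments at the 3-month visit, and at the 4-week outcome assessment if the footnote applies there. State which visits it covers. If Visit 4 means training session 4, say so.

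The cost is small: a reordering within existing visits, with no added staff, visits or procedures and no change for controls. Two limits remain. Experimental dyads already assessed will have had the earlier order, so with a mid-study change the order should be recorded for each dyad. Self-report bias from unblinded training and log-keeping also remains, so the change reduces the problem without removing it.

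The SAP is written in the past tense, so data collection may be complete. In that case, report the order of log review and caregiver interview by arm and visit as far as it is known, say so where it was not recorded, and qualify the six caregiver-reported outcomes accordingly.

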Study group: a functionally-tailored oral care intervention will be provided to the dyads. The goal of the intervention is to improve oral hygiene for PWD while reducing the burden of the caregiver. Different modules will be combined to provide personalized oral care interventions for PWD and their FCGs based on their needs. The following table provides a general guide to develop an oral care intervention based on PWD's oral self-care function. Note that the intervention will need to be individualized based dyad's needs.

Table 4 Functionally Tailored Oral Care Interventions Corresponding to Dental Activities Test (DAT) Scores

(DAT) Scores								
		endent core 9)	Needs Supervision (DAT Score 6-8)		Needs Assistance (DAT Score 3-5)		Full Care (DAT Score 0-2)	
	PWD⁵	Caregive	PWD	Caregiver	PWD	Caregiver	PWD	Caregiver
Goals of intervention	1. Regain/ Maintai n function 2. Improve quality of self- care	1. Ensure quality of care	2. Improv e quality of self- care	1. Ensure oral care quality 2. Provide assistance to facilitate oral self- care		1. Provide assistance to facilitate oral care 2. Provide oral care as needed 3. Ensure quality of care 4. Manage behavior symptoms		1. Provide oral care 2. Ensure quality of care 3. Manage disruptive behaviors 4. Identify PWD in pain or infection
Common intervention								needs (module 8,
Personalize d Modules**	1, 2	1, 3	2	1, 3, 4	2	1 - 5	N/A	1 - 6

^{*} ACLs-Allen Cognitive Levels; § PWD-Persons with dementia; ** Module 1-Oral disease and impacts; 2-Oral care techniques; 3-Quality improvement; 4-Cuing strategies; 5-working with behavior symptoms; 6-Recognizing oral pain/infection.

The intervention will consist of 4 sessions. The OCC will first assess dyad's oral care needs in the first visit and then develop the intervention protocol with [name] based on the guidance listed in table 3. The goals and intervention tasks of each visit are summarized in the following table.

Table 4. Tentative Intervention Sessions and Contents for the Control Group

Visit	Goal	Intervention Sessions and Contents for the Control Group Intervention				
	- 7	Reviews intervention program				
		Deliver Module 1.1 and 3.1 to the dyad				

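### Table 5 lists the probable oral care coach, jointly with the research assistant, as examiner for the Caregiver Interview, so burden, behavior and relationship scores may carry more courtesy bias in the intervention arm

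*Protocol*

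**What the plan says.** In Protocol Section VII, Table 5, the Caregiver Interview row for the repeated outcomes includes "Behavior symptoms during oral care Mouth Care Related Caregiver Burden Dyadic relationship", oral hygiene practice, and perceived oral hygiene and oral health. The family caregiver is the respondent, the times are baseline, 4 weeks and 3 months, and the examiners are LD and RA jointly. How the two divide the work is not stated.

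LD appears elsewhere in Table 5:
- sole examiner for the "First visit assessment form";
- sole examiner for the "Trainer evaluation questionnaire" at every session;
- sole examiner for the daily oral care log at every session and at 3 months;
- listed with the RA for the per-session feasibility questionnaires.

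Three entries go to other people. The Caregiver Self-efficacy Scale, at the same three time points, and the program-level feasibility questionnaires at 4 weeks are assigned to the RA alone. The plaque and gingival indices are assigned to a dentist.

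Section VI describes the coach (OCC) in both arms. For the study group: "The intervention will consist of 4 sessions. The OCC will first assess" the dyad's needs and then build the plan. For controls: "Control dyads will receive a 15-minute, home-based, untailored oral care training", after which "the OCC should allow participating dyads time to practice the oral care skills and provide real time feedback for the participants".

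The SAP compares the arms with unadjusted Wilcoxon rank-sum tests at each visit, and on raw and percent change from baseline for the primary outcomes.

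**The concern.** Burden, behavior symptoms and relationship quality are the caregiver's own judgments, given in an interview. A caregiver who has worked with a coach over four sessions may report more improvement to that coach than to a stranger. A control caregiver, trained once for 15 minutes, has less reason to.

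Section III names five example outcomes for Aim 2: oral hygiene, behavior symptoms, burden, self-efficacy and the care partner relationship. Three of these (behavior symptoms, burden, relationship) come from this interview. If part of the difference between arms reflects who asked the question, no analysis in the SAP can separate that part from a treatment effect. The per-session feasibility ratings raise a related problem, because the coach may be collecting ratings of the coach's own session.

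**Working it through.** The documents state no alpha, power, SD or effect size, so there is no figure of theirs to reproduce. The check is mainly a comparison of text.

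**Step 1. Is LD the coach?**

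| Task | Table 5 examiner | Section VI |
|---|---|---|
| First-visit form | LD alone | Visit 1, in a cell of tasks led by the OCC: "Complete the rest of the items in the First visit assessment" form |
| Daily log | LD alone, every session and 3 months | Handed out at session 2 and reviewed at session 3 |
| Trainer questionnaire | LD alone, every session (subject: trainer) | Sessions are given by the OCC |

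The session table used here has a caption naming the control group. It stands under the study-group text and sets out four visits, so it is read as the intervention schedule. Section VII says that the OCC and the RA visit participants. The RA is listed separately beside LD, which leaves the coach as the natural reading of LD.

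**Step 2. Is exposure to the coach unequal?** Yes: four hands-on sessions against one 15-minute training. Both arms meet the coach, so the difference is one of degree.

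**Step 3. Does change from baseline remove the bias?** Let the reported score be the true score plus a courtesy term c. The difference between arms in mean change is then

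true effect + (c at follow-up − c at baseline, intervention) − (c at follow-up − c at baseline, control).

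Section VII has baseline data collected before the intervention, so no coaching has yet taken place and the two baseline terms can be taken as equal. What remains is

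true effect + (c at follow-up, intervention − c at follow-up, control).

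The differential term stays in full. It is also present in the visit-by-visit comparisons.

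**Step 4. Would the interviewer know the arm?** Very likely. Section V assigns dyads to the intervention until 20 are reached and then to control. Section VII also has the note "if experimental group, collect and review oral care log before starting". The supplied text describes no blinding of interviewers.

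**Step 5. Illustration of size.** Inputs from the protocol: 20 dyads per arm. Assumptions: no true effect, two-sided alpha 0.05, normal scores, and a differential shift of b SD.

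Standard error of the difference in SD units = √(2/20) = 0.316.

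Rejection rate = Φ(b/0.316 − 1.96) + Φ(−b/0.316 − 1.96).

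| b (SD) | Upper tail | Lower tail | Normal approximation | Rank-sum simulation (3,000 runs) |
|---|---|---|---|---|
| 0.1 | 0.050 | 0.011 | 0.062 | not run |
| 0.2 | 0.092 | 0.005 | 0.097 | 0.096 |
| 0.3 | 0.156 | 0.002 | 0.158 | 0.157 |
| 0.5 | 0.352 | 0.000 | 0.353 | 0.328 |

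The two methods agree closely. At 0.5 SD the approximation is a little higher, as expected, because it treats the SD as known and the rank test is slightly less efficient for normal data.

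**The case against.** The strongest reply is that no document says the coach conducts these interviews. LD is undefined, and the contents of the roles table and several figures about visit procedures are not in the available text. Another row of Table 5 uses the label OCC beside RA, which suggests that LD could be someone else. The links are also not airtight. The bullet about the first-visit form names no subject, and the trainer questionnaire could be LD assessing another person. The RA may do all the follow-up interviewing. This stands, and it limits confidence to moderate. It does not dispose of the point: whoever LD is, Table 5 ties that person to every session, and the split with the RA is unstated.

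A reader might infer that the bias arises in one arm only. The documents do not support this. The coach also trains control dyads, with practice and feedback, and if LD is the coach, control caregivers also meet LD at the interview visits.

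A reader might also infer that all caregiver outcomes are affected. They are not, because self-efficacy is taken by the RA alone.

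Finally, the RA is no blinded stranger. The RA is listed for the session questionnaires and could infer the arm, and caregivers know what they received. An RA-only interview therefore removes the coach-specific part of the bias and no more. This also stands.

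**Conclusion.** The point holds in a conditional form. If LD is the coach, which is probable but inferred, Table 5 lets subjective caregiver outcomes be reported to, or in front of, someone with much more contact with intervention dyads than with control dyads. The resulting bias would be stronger in the intervention arm and would survive the change-score comparisons. It touches behavior symptoms, burden, relationship, oral hygiene practice and perceived oral health. It does not touch self-efficacy or the dentist-rated indices. The available SAP text does not say which outcomes are primary, so whether these scores enter the change comparisons is uncertain; the comparisons at each visit are exposed either way.

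The documents give no size for the bias. False-positive rates of about 10%, 16% and 33% belong to assumed shifts of 0.2, 0.3 and 0.5 SD. They would apply to a shift of that size from any source, and they do not show that this interview arrangement produces one. The change is worth making because it is cheap and the plan already uses the better arrangement for another scale.

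**What to change.** - Define LD in the protocol.
- In the Caregiver Interview row of Table 5, name the RA as sole examiner at baseline, 4 weeks and 3 months in both arms, with the person who coached the dyad not present. This copies the arrangement for the Caregiver Self-efficacy Scale. If LD must still review the log at a follow-up visit, LD should leave before the interview begins.
- Have the per-session feasibility questionnaires self-completed and not handed to the coach. Having the RA take them at every session would add to the RA's own contact with intervention dyads.
- Report as a limitation that neither the RA nor the caregiver is blinded, and that the RA is listed for session questionnaires.
- The SAP is written in the past tense. If the data are already collected, report by arm who conducted each follow-up interview and state the limitation.

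The cost is one table row, a line in the visit procedure and slightly more RA time per visit. No new staff are needed, since the RA already takes the self-efficacy scale at the same three time points.
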